Study Rationale	
From 1999 to 2015, the drug overdose death rate in non-metropolitan rural areas increased by 325% and, by 2015, exceeded that of metropolitan urban areas².Naloxone, an opioid overdose reversal agent, is not readily accessible in many rural communities.Community pharmacists are the most accessible healthcare professional in rural areas⁴⁻⁶ and are well-positioned to increase access to naloxone in rural areas⁷.The amount of naloxone dispensed by pharmacists has increased steadily over the past five years^{8,9}.Multiple studies¹¹⁻¹³ have shown that even when pharmacies stock naloxone, many pharmacists do not offer or dispense it. Reasons include barriers related to talking with patients and caregivers about the sensitive topic of overdose¹⁴⁻¹⁷.Pharmacists' comfort communicating about naloxone is significantly associated with how often they offer it¹³.Existing online naloxone training resources do not sufficiently address communication barriers.The objective of our 4-state collaboration is to develop an online module (Nalox-Comm) to increase rural pharmacists' self-efficacy to engage in naloxone discussions and, ultimately, increase how often they dispense naloxone.In Aim 1 (study #19-0998), we will gather and analyze formative data and engage in an iterative intervention development process to finalize Nalox-Comm content.For Aim 2 (study #20-2192), which is described in this protocol, we will conduct a pilot randomized controlled trial with 60 pharmacists to evaluate whether Nalox-Comm increases the frequency with which pharmacists dispense naloxone (primary outcome).
Study Objective(s)	
Primary
 
To evaluate whether Nalox-Comm increases the rate at which pharmacists dispense naloxone 
Secondary
 
To determine whether the Nalox-Comm module increases pharmacists' willingness to dispense naloxone

- To determine whether the module increases pharmacists' self-efficacy to dispense naloxone
- To determine whether the module improves the quality of pharmacists' naloxone communication

Test Article(s)	The Nalox-Comm training developed for this study is ~30 mins in length. It is an online module with videos, didactic content, and reflection. Content includes: 
 • The importance of naloxone and the role of the pharmacist • Non-stigmatizing language • How to initiate an offer of naloxone • How to respond to patient & caregiver naloxone requests • How to address specific communication barriers
Study Design	This is a cluster RCT with balanced randomization by pharmacy and two parallel groups (experimental and control), conducted with pharmacists from 62 pharmacies part of a single grocery store chain in rural counties of Georgia, North Carolina, South Carolina, and Tennessee.
Subject Population	Inclusion Criteria
key criteria for Inclusion and Exclusion:	
 1. Subjects age 18-99 years; 2. currently work at a pharmacy that stocks naloxone; 3. currently work at a rural community pharmacy; and 4. speak English. Exclusion Criteria 
 1. Non-staff pharmacists such as pharmacy "floaters" or fill-in pharmacists
Number Of Subjects	60 pharmacists
Study Duration	Each subject's participation will last approximately 6 months. The entire study is expected to last approximately 3 years.
Study Phases	
 1. Enrollment by invitation: inviting select pharmacies via email, confirming eligibility of those interested, obtaining electronic informed consent, completion of baseline survey 2. SP baseline observation: 3 SPs call each enrolled pharmacist to observe and rate the quality of their naloxone communication 3. Study intervention: participants complete either the Nalox-Comm module (experimental group) or the P2P training module (control group) based on previous randomization of pharmacies. They also complete a post-training survey. 4. SP post-training observation: 3 SPs call each enrolled pharmacist to observe and rate the quality of their naloxone communication

5. Follow-up: 3 months post-intervention, participants complete a final follow-up survey to assess secondary outcomes

Efficacy Evaluations	
Primary outcome: change in naloxone dispensing rates is measured by comparing pharmacy records of naloxone dispensed in the 3 months prior to study participation to number of naloxone dispensed in the 3 months after study completion
 
Secondary outcomes:
 
• Willingness – 7 items measure willingness to dispense naloxone. Pharmacists rate their willingness to engage in each item from 1= “Not at all willing” to 4 = “Very willing.”• Self-efficacy – factors were identified that could impact counseling self-efficacy. On the study surveys, pharmacists rate their confidence to engage in 7 naloxone communication tasks. Response options range from 1 = “Not at all confident” to 4 = “Very confident.”• Quality of naloxone counseling – SPs use a validated observation guide with 6 items to rate the pharmacist’s quality of communication on a 5-point scale (1 = lowest score and 5 = highest score).
Statistical And Analytic Plan	Linear regression using GEE will be used to assess the effect of the intervention on naloxone dispensing rates (primary outcome) after adjusting for any imbalances between the treatment groups. Similar models will be used to assess the effect of the intervention on each secondary outcome.
DATA AND SAFETY MONITORING PLAN	The study PI will evaluate data collected by secret shoppers and through surveys. The PI will also meet weekly with her project director and monthly with the research team to discuss data collection, potential data quality issues if they arise, and study progress. Also, the DSMB will provide an independent and unbiased review of the study’s ongoing progress.

BACKGROUND AND RATIONALE

In 2017, more than 49,000 of the 72,000 estimated drug overdose deaths in the U.S. involved opioid drugs¹. From 1999 to 2015, the drug overdose death rate in non-metropolitan rural areas increased by 325% and, by 2015, exceeded that of metropolitan urban areas². Naloxone, an opioid overdose reversal agent, is not readily accessible in many rural communities because these communities often lack substance use treatment resources and are health professional shortage areas³. Community pharmacists (pharmacists who work in outpatient ambulatory care settings) are the most accessible healthcare professional in rural areas⁴⁻⁶ and, due to statewide standing orders that have granted pharmacists increased prescriptive authority to dispense naloxone to anyone who may benefit from it, are well-positioned to increase access to naloxone in rural areas⁷.

The amount of naloxone dispensed by pharmacists has increased steadily over the past five years^{8,9}. This increase is likely to continue since the Surgeon General's (SG) Advisory on Naloxone and Opioid Overdose, which was released in April 2018, specifically encourages individuals to talk with their pharmacists about naloxone.¹⁰ Unfortunately, multiple studies^{11,12}, including our own¹³, have shown that even when pharmacies stock naloxone, many pharmacists do not offer or dispense it. The reasons behind pharmacists' reluctance to offer and dispense naloxone often include barriers related to talking with patients and caregivers (i.e., third parties who obtain naloxone for someone at risk of overdose) about the sensitive topic of overdose¹⁴⁻¹⁷. Our own work has shown that pharmacists' comfort communicating about naloxone is significantly associated with how often they offer it¹³. Existing online naloxone training resources do not sufficiently address communication barriers that may influence pharmacists' willingness to offer and dispense naloxone, particularly barriers that are common in rural areas, such as high stigma against drug use and fear of offending patients^{13,18}.

The objective of our 4-state collaboration is to develop an online module (Nalox-Comm) to increase rural pharmacists' self-efficacy to engage in naloxone discussions and, ultimately, increase how often they dispense naloxone. For Aim 1 (study #19-0998), we will gather formative data on barriers to engaging in naloxone conversations and preferences for module content from rural pharmacists, patients, and caregivers (i.e., third parties who obtain naloxone for someone who takes opioids). We will then analyze formative data and engage in an iterative intervention development process with a stakeholder development panel and expert consultants to finalize Nalox-Comm content. For Aim 2 (study #20-2192), which is described in this protocol, we will conduct a pilot randomized controlled trial with 60 pharmacists to evaluate whether Nalox-Comm increases the frequency with which pharmacists dispense naloxone (primary outcome). We will also assess whether the module increases pharmacists' willingness and self-efficacy to dispense naloxone and improves the quality of their naloxone communication (secondary outcomes).

1. STUDY OBJECTIVES

We are conducting a RCT to evaluate whether Nalox-Comm training increases how often rural pharmacists dispense naloxone compared to completing a more basic online naloxone training that includes minimal communication content. We hypothesize that pharmacists who complete Nalox-Comm will dispense more naloxone in the three months post-intervention (primary outcome) and will report greater willingness to dispense naloxone, higher naloxone counseling self-efficacy, as well as demonstrate higher quality communication about naloxone (secondary outcomes).

2. INVESTIGATIONAL PLAN

2.1 Study Design

This is a cluster RCT with balanced randomization by store and two parallel groups (experimental and control), conducted with pharmacists from 62 pharmacies part of a single grocery store chain in rural counties of Georgia, North Carolina, South Carolina, and Tennessee. These 62 pharmacies comprise all of the pharmacies in the grocery store chain that are in rural areas, defined by a Rural-Urban Commuting Area (RUCA) code of 4–10 and/or a county that is at least 33% rural according to the 2010 U.S. Census Bureau data¹⁹. Figure 1 provides an overview of the study design, including completion of a baseline survey, simulated patient baseline observations, an online experimental or control naloxone training, a post-training survey, simulated patient post-training observations, and a three-month follow-up survey.

2.2 Randomization and Allocation to Treatment Groups

All 62 rural pharmacies were matched based on their county's opioid prescribing rate and level of rurality (33% or greater). The county opioid prescribing rate for each pharmacy was identified using the Centers for Disease Control and Prevention's opioid prescribing rates²⁰.

Pharmacies were first ordered by opioid prescribing rate (primary matching variable) and then level of rurality. Pharmacies with exact matches were paired first and then the rest of the pairs were matched using the closest value. Using computer-generated random numbers, one pharmacy in each matched pair was randomized to either the control or experimental group.

2.3 Number of Subjects, Study Duration, and Enrollment

60 pharmacists, 30 for the experimental group (Nalox-Comm) and 30 for the control group (Prescribe to Prevent) will participate. The overall time commitment for participants is less than 2 hours spread out over a 6 month period. We will keep the study active until all aims are completed (approximately 3 years). The Clinical Coordinator for the grocery store pharmacy chain will distribute an email to the 62 rural pharmacy stores to notify pharmacists that the chain is participating in an evaluation of naloxone training materials and introduce them to the study team. The study team will then email the pharmacies' store email addresses with more information about the study and a link to an online baseline survey. The first page of the baseline survey contains a consent form, which notifies pharmacists that, should they choose to participate, they will be asked to complete surveys before and

after completing the training and will be observed by simulated patients. Pharmacists who provide electronic informed consent and complete the baseline survey are considered to be enrolled in the study. Upon completion of the baseline survey, they automatically receive an email confirmation detailing next steps.

2.4 Study Population

The recruitment goal is 60 pharmacists. Each of the 62 pharmacies employs two full-time pharmacists, both of whom can participate. Thus, participants for the RCT (N = 60) will be recruited from a total sample of 124 pharmacists. Eligible pharmacists must meet the following criteria: 1) be age 18 years or older, 2) speak English, 3) work as a full-time pharmacist at one of the participating 62 rural grocery store chain pharmacies. In addition, individuals who are a floater, or non-staff, pharmacist are ineligible.

3. STUDY PROCEDURES

3.1 Simulated patient pre-training observation

After completing the baseline survey and before receiving an invitation to complete the online naloxone training, three SPs who are blinded to group assignment call each enrolled pharmacist to observe and rate the quality of their naloxone communication. These SPs act as “Secret Shoppers”, whereby the pharmacist does not know the call is not a real patient. The SPs were trained using procedures that have been used in previous pharmacy SP studies²¹⁻²³. SPs were trained to present one of three realistic naloxone cases (i.e., scenarios). SPs were provided with a script, which they reviewed and practiced with the study team until their presentation felt genuine.

During and immediately after the interaction with the pharmacist, each SP rates several aspects of the encounter using an observation guide. SPs then enter their observation guide responses for each pharmacist into a secure Qualtrics survey where they do not have access to other SPs’ ratings for the same participant.

3.2 Naloxone online training

Once enrolled pharmacists have been observed by all three SPs, they receive an email invitation to complete either the Nalox-Comm module (experimental group) or the P2P training module (control group). The email includes a link to the respective training, instructions on how to navigate and complete the module, and the process for receiving continuing education (CE) credit. For those in the control group, the email also contains the link to the post-training survey, which is completed after training. The first question of this survey asks pharmacists if they completed the P2P training and will not allow them to continue the survey if they check “No.” Those assigned to the Nalox-Comm module (experimental group) are directed to the post-training survey within the module in order to coordinate CE credit and track completion.

3.3 Simulated patient post-training observation

Up to four weeks after pharmacists have completed training, the three blinded SPs observe their naloxone communication by phone a second time. In order to prevent pharmacists from recognizing

SPs, the three scenarios were adapted to be similar in nature to the pre-intervention scenarios, but different enough so as to not cause suspicion on the part of the pharmacist. SPs use the same observation guide to rate the pharmacists' naloxone communication and enter their responses into a secure Qualtrics survey.

To ensure SP scenarios are enacted with fidelity, research assistants observe two of each SP's baseline observations and two of their post-intervention observations, using an SP assessment guide to rate the quality of the SP's performance. Items in the guide were adapted from previously validated SP assessments^{24,25} and ask raters to indicate if all script content is covered and whether the SP sounds authentic and stays in his/her role. Additionally, research assistants describe any deviations and provide an overall rating from 1 to 9 of the SP's portrayal, where low numbers indicate "needs improvement" and high numbers indicate a "great" portrayal.

3.4 Three-month post-intervention follow-up

When three months has passed since training, pharmacists receive an email invitation to complete their final follow-up survey, which assesses the study's secondary outcomes.

3.5 Remuneration and participant follow-up

Participants can receive up to \$150 in Amazon eGift cards for completing the study: \$50 for completing each of the surveys (baseline, post-training, and three-month follow-up). To help reach the enrollment goal of 60 pharmacists, as well as ensure a 100% completion rate for those enrolled, up to five follow-up email reminders are sent to non-completers of each survey. If no response is received after the reminder emails, pharmacists receive one phone call. Additionally, recruitment flyers were mailed to each pharmacy.

4. STUDY EVALUATIONS AND MEASUREMENTS

4.1 Primary outcome

Our primary outcome is change in naloxone dispensing rates measured by comparing pharmacy records of naloxone dispensed in the three months prior to study participation to number of naloxone dispensed in the three months after study completion (Table 2). The grocery store pharmacy chain has agreed to provide us with these naloxone dispensing rates from each of the participating pharmacies at the conclusion of the study. We hypothesize that pharmacies in the experimental group will dispense more naloxone in the three months post-intervention compared to pharmacies in the control group.

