5.1 Primary outcome

The GEE method will be used to detect a significant difference in our primary outcome variable of frequency of naloxone dispensing. Specifically, we will evaluate change in naloxone dispensing from the 3 months pre-intervention to the 3 months post-intervention. Our multivariable model will be nested by pharmacy and will include several covariates, including the county’s opioid prescribing rate, pharmacy rurality, average daily script fill rate, and demographic characteristics of the pharmacist. Alpha will be set at 0.05.

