5.3 Sample size and power

Pharmacies in this grocery store chain dispense naloxone once for every 250 opioid prescriptions, on average. With 60 pharmacists, 30 per treatment arm, we have at least 80% power at the 0.05 significance level to detect an increase in naloxone dispensing to 1 for every 100 opioid prescriptions dispensed, assuming a standard deviation of 0.008 (2 in 250 or 0.8 in 100) and depending on the intraclass (within pharmacy) correlation. In other words, we expect the intervention to increase the naloxone dispensing rate from 1 in 250 (0.4%) to 1 in 100 (1%), an increase of 0.6%. So, the sample size is based on a mean difference of 0.6%.

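### The primary change score rests on one 3-month baseline that is not a named covariate; a longer look-back in the same record extraction, used as a covariate, would probably buy precision cheaply

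*Combined protocol and SAP*

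**What the plan says.** Section 4.1 obtains the primary outcome by "comparing pharmacy records of naloxone dispensed in the three months prior to study participation" with the "number of naloxone dispensed in the three months after study completion". The synopsis gives the same two windows. Section 5.1 states the analysis as a change: "we will evaluate change in naloxone dispensing from the 3 months pre-intervention to the 3 months post-intervention". The GEE model "will include several covariates, including the county’s opioid prescribing rate, pharmacy rurality, average daily script fill rate, and demographic characteristics of the pharmacist". Pre-period dispensing is not among the covariates named.

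On the source, section 4.1 says that the chain "has agreed to provide us with these naloxone dispensing rates from each of the participating pharmacies at the conclusion of the study". No section explains why three months was chosen or plans a longer baseline.

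Section 5.3 gives the scale: "Pharmacies in this grocery store chain dispense naloxone once for every 250 opioid prescriptions, on average". It assumes a standard deviation of 0.008 and a rise from 0.4% to 1%, and states: "With 60 pharmacists, 30 per treatment arm, we have at least 80% power at the 0.05 significance level". It does not say whether 0.008 is the SD of a single 3-month rate or of the change.

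**The concern.** A post-minus-pre difference carries the random error of both windows. If both windows are equally noisy, half of the within-store error comes from the baseline. Dispensing is probably sparse: the mean rate is 0.004 and the assumed SD is twice that. Opioid prescription volume per store is not given, so sparseness is an inference. With an assumed 250 to 1,000 opioid prescriptions per store per quarter, 1 per 250 means 1 to 4 naloxone fills.

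Section 2.1 says that the 62 stores are all of the chain's rural pharmacies, so precision cannot come from adding stores. Baseline noise, by contrast, can be reduced from records that should already exist, with no further contact with pharmacists. What is at stake is the precision of the primary comparison.

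**Working it through.** **1. The plan's own figure.** Inputs from section 5.3: 30 per arm, difference 0.006, SD 0.008. Section 5.1: "Alpha will be set at 0.05", taken as two-sided. The standard error is 0.008 × √(2/30) = 0.002066, and 0.006/0.002066 = 2.905. Power is Φ(2.905 − 1.960) = 82.8% (81.5% with the noncentral t). The stated 80% reproduces when within-pharmacy correlation is close to zero.

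**2. Change score, equal correlation.** Let each quarter's rate have variance v and every pair of quarters correlation ρ.
- 3-month baseline: 2v(1 − ρ)
- 12-month baseline (mean of four quarters): (1 + 1/4)v(1 − ρ) = 1.25v(1 − ρ)

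The ratio is 1.25/2 = 0.625 for any ρ, a cut of 37.5%. Six months gives 1 − 1.5/2 = 25%, and nine months gives 1 − (4/3)/2 = 33%.

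**3. Change score, planned effect, Poisson noise.** Variance is proportional to the rate (units of 0.1%, equal volumes).
- Control: 4 + 4 = 8 becomes 4/4 + 4 = 5.
- Experimental: 4 + 10 = 14 becomes 4/4 + 10 = 11.
- Contrast: 22 becomes 16, a cut of 27%.

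**4. Change score, first-order autocorrelation φ, adjacent windows.** The 3-month variance is 2(1 − φ). The 12-month variance is 1 + [4 + 2(3φ + 2φ² + φ³)]/16 − (φ + φ² + φ³ + φ⁴)/2.

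| φ | 3-month | 12-month | Change in variance |
|---|---|---|---|
| 0.1 | 1.80 | 1.235 | −31% |
| 0.2 | 1.60 | 1.211 | −24% |
| 0.3 | 1.40 | 1.176 | −16% |
| 0.5 | 1.00 | 1.047 | +5% |

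The gain disappears near φ = 0.45.

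**5. Baseline as a covariate, equal correlation, v = 1.** Residual variance is 1 − ρ² with 3 months. With 12 months, the baseline mean has variance (1 + 3ρ)/4 and covariance ρ with the post-period, so the residual is 1 − 4ρ²/(1 + 3ρ).

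| ρ | 3-month change, 2(1 − ρ) | 3-month covariate | 12-month covariate | Further cut, 3 to 12 months |
|---|---|---|---|---|
| 0.2 | 1.60 | 0.96 | 0.90 | 6% |
| 0.5 | 1.00 | 0.75 | 0.60 | 20% |
| 0.8 | 0.40 | 0.36 | 0.247 | 31% |

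At low correlation most of the improvement over the planned change score comes from adjustment itself (1.60 to 0.96). At high correlation most comes from the longer baseline (0.36 to 0.247).

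**6. Which form of covariate.** Under first-order autocorrelation with adjacent windows, replacing the latest quarter by the 12-month mean raises residual variance by 1%, 3%, 7% and 19% at φ = 0.1, 0.2, 0.3 and 0.5. Entering the latest 3 months and the earlier 9 months as two terms avoids this. In that setting the earlier months add nothing once the latest quarter is in the model, so the cost is one degree of freedom. Under equal correlation the two terms can reproduce the 12-month mean and keep its gain.

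**The case against.** The case against is substantial. Equal 3-month windows are stated consistently in a trial that calls itself a pilot, nothing contradicts itself, and no estimate is biased. This stands: the point is one of efficiency.

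A cheaper remedy exists. Adjusting for the 3-month baseline already planned needs no new data, and it beats a 12-month change score whenever 1 − ρ² < 1.25(1 − ρ), that is, ρ < 0.25. Low correlation is what sparse counts tend to produce. This also stands, and it is why the longer baseline should enter as a covariate. It would be wrong to say that extending the baseline is the only inexpensive way to reduce variance. The covariate list in section 5.1 is open-ended and the synopsis adjusts for imbalances, so baseline adjustment is not excluded; it is simply not specified.

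Availability is unproven. The chain agreed to supply the rates described in section 4.1, and nothing shows that 12 months of monthly counts are available or agreed. Eligibility requires only that the pharmacist currently works at a pharmacy that stocks naloxone, so older months may predate the stock or the pharmacist. The background also describes rising dispensing. Such changes can erode the gain, but they do not bias a comparison between randomised stores.

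A reader might also infer that season confounds the result because the two windows fall at different times of year. The concurrent randomised control arm handles seasonality common to both arms, so that argument is not available.

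**Conclusion.** The point holds as a missed efficiency in the primary analysis. As written, the plan lets the noise of a single 3-month baseline enter in full and does not specify adjustment for it.

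The figure of 37.5% is a ceiling for a change score with equally variable, equally correlated quarters. A reader might take it as the expected gain, and the documents do not support that. The cut is about 27% under the plan's own effect with Poisson noise, and under autocorrelation it can be much smaller or become a small loss. With baseline as a covariate, the further gain from 12 months is 6% to 31% for equal correlations of 0.2 to 0.8.

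A reader might also want one figure for the power gained. The documents do not fix one, because the SD of 0.008 is not labelled. With the full 37.5% cut and no clustering, power would go from 82.8% to 95.7% if 0.008 is the SD of the change. It would go from 53.7% to 73.8% if 0.008 is the SD of a single window with uncorrelated quarters. These are best cases for the change score.

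The between-quarter correlation, the store volumes and the availability of older records are all unknown. A longer baseline also does nothing about analysing a pharmacy-level outcome per pharmacist.

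**What to change.** Before the extraction, and before anyone sees dispensing by arm, amend sections 4.1 and 5.1 as follows.

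- Ask the chain for monthly naloxone and opioid-prescription counts for up to 12 months before each store's start, with that start date defined in advance. The opioid counts also supply the denominator that the rate in section 5.3 needs.
- Keep the 3-month post window.
- Model the post-period rate with the pre-period rate as a pre-specified covariate: either the 12-month rate, or the latest 3 months and the earlier 9 months as two terms. The two-term form is safer if dispensing drifts.
- Report the 3-month change as now defined as a sensitivity analysis.

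The cost is one wider data request, a short amendment and at most two model terms. Availability must be confirmed with the chain first; if only 6 or 9 months can be had, part of the gain remains. If nothing beyond 3 months is available, naming the 3-month baseline as a covariate is still worth doing and needs no new data. The downside is that older months may represent a store less well if its dispensing, staffing or stocking has changed.
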